7.1. Schedule of visits and Study Assessments for non-cirrhotic patients

					On-Treatment Study Visits 12 weeks				R12)	4)	(ts ¹³
Evaluations / study procedures / study visit ¹	Eligibility (45 days to day -1)	Screening (30 days to day -1)	Day 1	Treatment Visit Wk. 1 +/- 3days	Treatment Visit wk. 4 +/- 7days	Treatment Visit wk. 8 +/- 7days	Treatment Visit W12 (End of Treatment or premature discontinuation) +/- 7days	Follow-up visit wk. 4 (SV (-1 day and +7 days)	Follow-up visit wk. 12 (SVI (-1 day and +28 days)	Follow-up wk.24 (SVR2 (-3 days and +28 days)	Long term Follow-up visit (-28 days and +28 days)
Information, counselling	X ²	Х									
Informed consent	Х										
Inclusion/exclusion criteria & demography		Х									
HCV, HBsAg, HIV	Х										
Medical history, full clinical examination ³ Height Weight		х									
Symptom directed assessment			Х	Х	Х	Х	Х	Х	Х	Х	Х
Concomitant medication review		Х	Х	Х	Х	Х	Х	Х	Х	Х	
AE review			Х	Х	Х	Х	Х	Х	Х	Х	Х
Vital signs		Х	Х	Х	Х	Х	Х	Х	Х		
Fibroscan ⁴		Х									X4
12 leads ECG		Х		Х			Х	X ¹⁴			
Hematology (full blood count)		Х	Х		Х	Х	Х	Х	Х		Х
Chemistry (alkaline phosphatase, serum albumin, direct/total bilirubin, ALT/ AST, serum creatinine)		х	х		х	х	х	х	х	X ¹²	Х
Fasting blood sugar (glucose)		Х									
Coagulation (PT, INR)		Х								Х	
Urinalysis		Х							Х		
Urine pregnancy tests ⁵		Х	Х	Х	Х	Х	Х	Х			
HCV RNA	Х			X ⁶	X ⁶	X ⁶	X ⁶	X ^{6a}	X ⁶	Х	Х
HIV RNA ⁷		Х							Х		
CD4 count ⁷		Х							Х		
HCV genotype		Х									Х
Stored Plasma and DBS ⁸	Х	Х	Х	Х	Х	Х	Х	Х	Х	Х	Х

				On-Treatment Study Visits 12 weeks					R12)	24))
Evaluations / study procedures / study visit ¹	Eligibility (45 days to day -1)	Screening (30 days to day -1)	Day 1	Treatment Visit Wk. 1 +/- 3days	Treatment Visit wk. 4 +/- 7days	Treatment Visit wk. 8 +/- 7days	Treatment Visit W12 (End of Treatment or premature discontinuation) +/- 7days	Follow-up visit wk. 4 (SV (-1 day and +7 days)	Follow-up visit wk. 12 (SV (-1 day and +28 days)	Follow-up wk.24 (SVR2 (-3 days and +28 days	Long term Follow-up vis (-28 days and +28 days
Resistance testing ⁹		Х									
PK Intensive Sampling (stage 1 only) ¹⁰					Х						
PK sparse sampling ¹¹					Х	Х	Х				
Predose ARV PK sample for subjects on ART			Х								
Hair sampling		Х					Х				
Adherence				Х	Х	Х	Х				
Study Drug Dispensing			Х		Х	Х					
PROQOL-HCV			Х			Х			X		

¹ Eligibility and screening can be done on the same day for already HCV diagnosed subjects

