7.2. Schedule of visits and Study Assessments for cirrhotic patients

		Screening period (within 30 days to day -1)	Day 1		On	I-Treatm 24	ent Study Weeks	_	5 (4 S)	
Evaluations / study procedures / study visit ¹	Eligibility (45 days to day -1)			Treatment Visit wk. 1 +/- 3days	Treatment Visit wk. 4 +/- 7days	Treatment Visit wk. 8 +/- 7days	Treatment Visit Wks 12, 16 ,20 +/- 7days	Treatment Visit wk. 24 (END of Treatment Premature discontinuation) +/- 7days	Follow-up visit wk. [,] (SVR4) (-1 day and +7 days) Follow-up visit wk. 1	Follow-up visit wk. 1: (SVR12) (-1 day and +28 days)	Follow-up W24 (SVR2 (-3days and +28 days	Long term FU visits (-28 days and +28 da)
Information, counseling	X ²	Х										
Informed consent	Х											
Inclusion/exclusion criteria & demography		Х										
Medical history, full clinical examination ³ Height/Weight		Х										
HCV, HBsAg, HIV	Х											
CTP score ⁵		Х	Х	Х	Х	Х	Х	Х	Х	Х	Х	Х
Symptom directed assessment			Х	Х	Х	Х	Х	Х	Х	Х	Х	Х
Vital signs		Х	Х	Х	Х	Х	Х	Х	Х	Х		
Conc. medication review		Х	Х	Х	Х	Х	Х	Х	Х	Х	Х	
AE review			Х	Х	Х	Х	Х	Х	Х	Х	Х	Х
Fibroscan ⁴		х					Wk:12 only			Х	Х	X ⁴
12 leads ECG		Х		Х				Х	X ¹⁵			
Hematology (full blood count)		Х	Х		Х	Х	Х	Х	Х	Х		Х
Chemistry (alkaline phosphatase, serum albumin, direct/total bilirubin, ALT/ AST, serum creatinine)		х	х		х	х	х	Х	х	х	X ¹³	Х
Fasting blood sugar (glucose)		Х										
Coagulation Markers (PT, INR) ⁵		Х	Х		Х	Х	Х	Х	Х	Х	Х	X ⁵
Urinalysis		Х								Х		
Urine pregnancy tests ⁶		Х	Х	Х	Х	Х	Х	Х	Х			
HCV RNA	Х			X7	X ⁷	X7	X7	X ⁷	X ^{7a}	X7	Х	Х
HIV RNA ⁸		Х								Х		
CD4 count ⁸		Х								Х		
HCV genotype		Х										Х
Resistance testing ⁹		Х										

Evaluations / study procedures / study visit ¹	Eligibility (45 days to day -1)	-1)			On	-Treatm 24	ent Study Weeks	v Visits	+	~ 7	Follow-up W24 (SVR24) (-3days and +28 days)	Long term FU visits ¹⁴ (-28 days and +28 days)
		Screening period (within 30 days to day -	Day 1	Treatment Visit wk. 1 +/- 3days	Treatment Visit wk. 4 +/- 7days	Treatment Visit wk. 8 +/- 7days	Treatment Visit Wks 12, 16 ,20 +/- 7days	Treatment Visit wk. 24 (END of Treatment Premature discontinuation) +/- 7days	Follow-up visit wk. ² (SVR4) (-1 day and +7 days)	Follow-up visit wk. 1 (SVR12) (-1 day and +28 days		
Stored Plasma and DBS ¹⁰	Х	Х	Х	Х	Х	Х	Х	Х	Х	Х	Х	Х
Intensive PK Sampling (stage 1 only) ¹¹					Х							
PK sparse sampling ¹²					Х	Х	Х					
Predose ARV PK sample for subjects on ART			Х									
Hair sampling		Х						Х				

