Adherence				Х	Х	Х	Х	Х				
Study Drug Dispensing			Х		Х	Х	Х					
PROQOL-HCV			Х			Х				Х		

¹ Eligibility and screening can be done on the same day for already HCV diagnosed subjects

² For subjects tested for the first time for HCV, extensive information and counselling perform HCV serology and confirm HCV chronic infection.

³ At screening a full clinical assessment is required and the signs or symptoms of hepatic decompensation must be documented. On other visits-a symptom directed assessment is required. In addition, for the cirrhotic group features of decompensation like ascites or hepatic encephalopathy need to be assessed and the CTP score calculated.

⁴ Fibroscan can be conducted at Screening visit or baseline FibroScan within 12 months to screening maybe use to assign treatment duration. A repeat FibroScan will be done at treatment W12 and W12 and W24 post treatment visits. A F broscan can also performed at all long term follow-up visits (until one year after end of treatment for patients cured and until 3 years after end of treatment for non-cured patients- see details of assessments in section 13.5.2).

⁵ CTP and coagulation tests are applicable to cirrhotic patients only and score based on the CTP score chart provided. Cirrhotic patients must continue their HCC surveillance program and any finding of HCC is suspected/confirmed to report as AE. A coagulation test can also performed at all long term follow-up visits (until one year after end of treatment for patients cured and until 3 years after end of treatment for non-cured patients- see details of assessments in section 13.5.2)

⁶ Urine pregnancy test to be done for women of child bearing age

⁷ For stage 1, HCV RNA will be performed on stored samples if SVR12 is not achieved or on any patient at any time if needed. For stage 2, HCV RNA will be performed on all samples on an ongoing basis at each treatment visit.

^{7a} Will be performed on stored samples for all patients

⁸ For HIV positive cases only (HIV monitoring (CD4 and viral load) is part of the standard of care for HIV subjects enrolled in the study. Closer follow-up performed upon clinical judgment of the principal investigator will be paid by the study).

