9.7. Discontinuation and interruption of treatment

Treatment may be discontinued:

- upon request of the subject, following counselling on the potential consequences and risks of antiviral discontinuation
- upon request of the primary care provider if s/he thinks that the it is no longer in the best interest of the subject,
- if, after discussion with the study team, the investigator judges that the subject is at significant risk of failing to comply with the provisions of the protocol thus compromising the validity of the study results,

- in case of HCV virological failure,
- in occurrence of serious adverse events deemed to be related to the study drugs or possibly interfering with therapy and upon consultation with the DSMB. Patient's follow-up will continue as follow-up visits in protocol and unscheduled visits are allowed as decided by investigators.
- upon recommendation of the Data and Safety Monitoring Board (DSMB) and,
- at the discretion of the IRB, relevant regulatory agency, any other government agency as part of their duties to protect the welfare of subjects

The study team must be informed, as soon as possible, when a subject comes off study treatment due to an AE. Restart of treatment after any interruption must be discussed and agreed on a case by case basis with the investigator and agreed with the sponsor.

Subjects who prematurely discontinue study treatment (i.e., prior to completion of their assigned dosing period) will complete all end of treatment evaluations, will remain on study and complete all post treatment visits, except if they have withdrawn consent.

If applicable, additional unscheduled post-treatment safety follow-up will be determined by the site investigator.

In stage 2, the following treatment stop criteria^[65] will apply for any patient from stage 2 study with:

- ALT/AST > 8x ULN
- ALT/AST remains > 5x ULN over 2 wks
- ALT/AST > 3x ULN & T Bili > 2x ULN or INR > 1.5
- ALT/AST > 3x ULN with symptoms (e.g. fatigue, nausea and vomiting, right upper quadrant of abdomen pain, fever, rash) or eosinophilia

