Generally, rechallenge of subjects with significant ALT/AST elevations (>5xULN) should not be attempted. If such subjects are rechallenged, they should be followed closely. Rechallenge can be considered if the subject has shown important benefit from the drug and other options are not available or if substantial accumulated data with the test drug do not show a potential for severe injury. The subject should be made aware of the potential risk, and consent to the rechallenge, and the institutional review board consulted.

A DSMB meeting will be set up in case one patient meets any of the above listed criteria, which is considered as a major safety signal.

10. Baseline Assessments

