16.1. Sample size determination

A WHO publication^[71] describes the ideal HCV treatment as having efficacy \geq 85% in all populations in a public health setting, while DNDi's target product profile sets an acceptable real world effectiveness target of \geq 80% with 12 weeks' treatment for non-cirrhotics and 24 weeks for those with compensated cirrhosis.

16.1.1. Sample size determination for stage 1

Stage 1 of this study will be intended to give a clear indication of likely real world effectiveness. It is recognised that some sub-groups of HCV patients are more difficult to cure than others. This includes those with cirrhosis (particularly when infected with genotype 3 virus), those co-infected with HIV and those who have failed previous treatment. Within these categories, only subjects with decompensated cirrhosis and those with prior treatment with an NS5A inhibitor will be excluded. No restrictions will be imposed on the number of subjects in each sub-group and subjects with more than one of the difficult to treat characteristics (for example treatment experienced, GT3, and with compensated cirrhosis) can be enrolled. As a consequence, it is not expected that the efficacy in this study to reach the levels that could be achieved in studies with much tighter inclusion criteria. Based on published results for other treatments, we considered that the overall SVR12 rate should be superior to 85%. A sample size of 300 subjects in Stage 1 will ensure that the width of the exact Clopper-Pearson 95% confidence interval (CI) around the overall SVR12 rate expected to be observed is as small as 6-7% (see table below). It would provide over 86% power to detect at least 6% improvement in the overall SVR12 rate from this pre-specified performance goal of 85%, using a two-sided exact one-sample binomial test at a significant level of 0.05. With this sample size, the lower bound of the 95% CI will be greater than 85% if the observed overall SVR12 rate is 90% or higher.

16.1.2. Sample size determination for stage 2

As there are no changes to the design for Stage 2, a further 300 subjects will be recruited in Stage 2. The objective of Stage 2 is to provide further data on the efficacy and safety of SOF-RDV in all key subgroups. Additional subjects will be enrolled in order to reach ideally 50 subjects per subgroup (30 for GT2) when combining both stages.

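### The INR limb of the Stage 2 liver stop rule has no scheduled or triggered INR behind it in non-cirrhotic subjects on treatment

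*Protocol*

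**What the plan says.** Section 9.7 introduces "the following treatment stop criteria" for Stage 2 and applies them to any Stage 2 patient, with or without cirrhosis. There are four. The third is "ALT/AST > 3x ULN & T Bili > 2x ULN or INR > 1.5". The consequence goes beyond the individual: "A DSMB meeting will be set up in case one patient meets any of the above listed criteria", and 9.7 treats that as a major safety signal.

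Two tables fix the laboratory schedule. In 7.1 (non-cirrhotic), the row beginning "Coagulation (PT, INR" is marked at screening and follow-up week 24 only. The row beginning "Chemistry (alkaline phosphatase, serum albumin, direct/total bilirubin, ALT/ AST, serum creatinine" is marked at Day 1 and at weeks 4, 8 and 12 on treatment, as well as at screening and follow-up. In 7.2 (cirrhotic), the row beginning "Coagulation Markers (PT, INR" is marked at Day 1 and at every on-treatment visit except week 1. Footnote 5 of 7.2 adds that "CTP and coagulation tests are applicable to cirrhotic patients only".

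**The concern.** A mandatory stop rule should draw on measurements that the protocol collects or tells the site to collect. Bilirubin and ALT/AST meet that test in both strata. INR meets it only in cirrhotics. In non-cirrhotics the sponsor has written INR as an alternative to bilirubin but has not said when anyone should measure it during dosing.

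Two things are at stake. One patient with a rise in ALT/AST and an INR above 1.5 could continue dosing at a site that orders no INR and be stopped at a site that does. The DSMB meeting that a single case should trigger could also fail to happen. Neither SVR12 nor any planned analysis is affected; this is a point about patient safety and consistent conduct.

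**Working it through.** The plan gives no figure to reproduce, so the check sets the rule against the schedules and then looks for any text that closes the gap.

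**Step 1: what is drawn during dosing** (visit columns of 7.1 and 7.2).

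| Visit | Chemistry, non-cirrhotic | PT/INR, non-cirrhotic | Chemistry, cirrhotic | PT/INR, cirrhotic |
|---|---|---|---|---|
| Day 1 | yes | no | yes | yes |
| Week 1 | no | no | no | no |
| Week 4 | yes | no | yes | yes |
| Week 8 | yes | no | yes | yes |
| Week 12 | yes (end of treatment) | no | yes | yes |
| Weeks 16, 20, 24 | not applicable | not applicable | yes | yes |

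Chemistry visits after Day 1 with a paired INR: non-cirrhotic 0 of 3 (weeks 4, 8, 12); cirrhotic 6 of 6 (weeks 4, 8, 12, 16, 20, 24). Non-cirrhotic dosing lasts 12 x 7 = 84 days, and the schedule requires no INR within it. The cirrhotic INRs also serve CTP scoring. The contrast therefore shows where the input exists, not that someone judged INR unnecessary in non-cirrhotics.

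**Step 2: is there a triggered test elsewhere?**

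- 9.7 lists the criteria but does not order an INR when ALT/AST is raised.
- 10.7 lists PT and INR among baseline tests.
- 13.4 (on-treatment visits) does not mention INR.
- 15.3 repeats the abnormal test and, for a confirmed and related Grade 3 laboratory toxicity, holds treatment and follows laboratory values weekly. It does not name INR and does not start from ALT/AST above 3x ULN.
- 13.5.2 adds INR in non-cirrhotic virological failures, but from one year after the end of treatment.

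None of these closes the gap.

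**Step 3: which patient falls through?** Take the third criterion as ALT/AST above 3x ULN together with either bilirubin above 2x ULN or INR above 1.5. INR decides only if nothing else already stops or holds treatment. All of these must then be true of a Stage 2 non-cirrhotic with INR above 1.5:

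1. ALT/AST above 3x but not above 8x ULN (otherwise the first criterion applies).
2. ALT/AST not staying above 5x ULN over 2 weeks (second criterion).
3. Bilirubin at or below 2x ULN (bilirubin limb of the third).
4. No symptoms and no eosinophilia (fourth).
5. Not already on hold under 15.3 for a confirmed related Grade 3 laboratory toxicity.

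**Step 4: when does it matter?** Of the three chemistry visits, stopping shortens dosing at two, weeks 4 and 8. Week 12 is the end-of-treatment visit, so only the DSMB trigger remains there.

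**Step 5: how often?** The protocol gives no rate for ALT/AST above 3x ULN on treatment and none for INR above 1.5 in non-cirrhotics. No frequency can be derived.

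**The case against.** The best answer is that 9.7 itself prompts the test. An investigator who sees ALT/AST above 3x ULN with bilirubin not above 2x cannot tell whether the third criterion is met without an INR. Site laboratories already run coagulation tests (14.4), and nothing forbids an unscheduled one. This stands in large part. A reader might infer that the rule cannot operate in non-cirrhotics, or that a site following the protocol can never obtain the INR. The documents do not support that: the step is unstated, not blocked. What remains is that no sentence obliges it.

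Other safeguards also narrow the case. The 15.3 hold may cover part of the band between 3x and 8x ULN. How much cannot be checked, because the DAIDS grading table is not reproduced in Appendix II. It would therefore go too far to say that INR is the only finding that could interrupt treatment anywhere in that band. The symptom list in the fourth criterion is open-ended and includes fatigue and nausea, which section 2.3 names among the most frequent reactions.

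Two further strong readings are tempting. One takes the unbracketed criterion to mean that INR above 1.5 alone stops treatment. All four criteria open with ALT/AST, and the rechallenge text in 9.7 concerns ALT/AST elevations, so that reading is strained; brackets would simply remove it. The other takes footnote 5 of 7.2 as a bar on testing non-cirrhotics. It is a note to the cirrhotic table, and the coagulation row of 7.1 and the long-term follow-up table in 13.5.2 both contradict it if it is read literally. It is loose wording.

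**Conclusion.** The mismatch is real and minor. A mandatory stop criterion for all Stage 2 patients includes an input that the non-cirrhotic schedule does not supply between screening and follow-up week 24, and that no rule triggers. Its detection is left to investigator discretion, at two visits where a stop would still shorten dosing and a third where only the DSMB meeting is at issue. The bilirubin limb and the first criterion work from scheduled chemistry. The same chemistry detects the ALT/AST rise behind the other two, and full blood count is drawn at the same visits.

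This rests on reading the criterion as ALT/AST together with bilirubin or INR. It also assumes that no operational document supplies the missing instruction. The Manual of Operations is not shown; the protocol cites it for an eligibility criterion, not in 9.7. The number of stop signals that could be missed cannot be estimated.

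**What to change.** In 9.7, and as a footnote to the coagulation row of 7.1, require a PT/INR whenever a Stage 2 non-cirrhotic subject's on-treatment ALT/AST exceeds 3x ULN, from the same sample or a prompt repeat draw, for example within 1 week. Bracket the criterion as ALT/AST > 3x ULN AND (T Bili > 2x ULN OR INR > 1.5). With the brackets, the ALT/AST trigger covers every case in which INR matters. Rewording footnote 5 of 7.2 is optional tidying.

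The cost is one sentence, one footnote, a pair of brackets and what should be a small number of extra INRs at laboratories that already run them. That number cannot be estimated from the document. Only ALT/AST above 10x ULN excludes a subject, so some may enter already above 3x and trigger the test on baseline disease. A triggered test is still lighter than routine INRs at weeks 4, 8 and 12, which would add three per non-cirrhotic subject completing treatment.

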10.1. Information

Information and education materials will be used to raise awareness about HCV, the short and long term morbidity associated with chronic infection as well as the availability of short, highly effective, interferon/ribavirin free treatment courses with cure rates above 90%. Each site will develop its recruitment scheme according to locally relevant risk factors.

10.2. Counseling

Interested subjects will receive further information and counseling about HCV, co-infections, the implications of a positive test, as well as the practical details of the study. Consenting subjects will be tested for HCV serology, and if positive serology for HCV RNA. An appointment will be made to discuss the results and implications of this eligibility phase.

10.3. HCV testing

A quantitative HCV RNA viral load is essential to confirm that subjects with a positive HCV antibody test have chronic HCV infection, and establish pre-treatment baseline viral load levels. Blood sample for HCV RNA PCR testing will be collected, processed, and shipped to the designated laboratory. Results will be reported within 2 weeks after specimen receipt. Additional plasma will be stored to allow confirmatory tests: genotyping, viral load, presence of prescribed or non-prescribed drugs.

HCV chronic infection confirmation and initial evaluations

HCV RNA positive patients will be further explained the study process including baseline evaluations, the need for referral to the academic/dedicated site for liver fibrosis staging or on-site appointment for fibrosis staging depending on availability of the Fibroscan equipment and/or the results of APRI score, nature and duration of treatment dependent on the presence/absence liver cirrhosis and potential side-effects. They will also be explained all study clinical and biological procedures up through the end of the study visit (i.e. post-treatment follow-up Week 24 or end of long term follow-up for subset of cured patients or patients with virological failure).

10.4. Medical history

Medical history will focus on:

- Risk factors for HCV acquisition including injection drug use (IDU), receipt of a blood/blood products transfusion prior to universal HCV infection screening for blood donation, needle stick injury, tattooing, body piercing, mother-to- child transmission, sexual transmission among men who have sex with men (MSM), particularly men with HIV infection.
- Psychiatric History: Patients with HCV infection have a higher incidence of psychiatric illness compared with the general population; inadequately treated psychiatric illness represent a barrier to successful HCV therapy.
- Medical Comorbidities / extrahepatic manifestations: all medical history need to be documented in particular diabetes, any diagnosis of kidney disease (nephropathy, glomerulonephritis), thyroid disease, skin disease (livedo reticularis, lichen planus, and cold agglutinin disease), arthralgia, neuropathy or non-alcoholic fatty liver disease (NAFLD).
- Coinfections: Hepatitis B virus (HBV), and human immunodeficiency virus (HIV).
- Complications of liver Disease: ascites including diuretic controlled ascites, hepatic encephalopathy, jaundice, hepatocellular carcinoma or variceal bleeding. CTP scoring will be performed.
- Prior Treatment for Hepatitis C.
- Documentation of the types of treatment received previously and types of response i.e.
 - 1. non responders (HCV RNA detected at the end of treatment) or
 - 2. relapsers (HCV RNA not detected at the end of treatment but detected at any time within 24 weeks post treatment or
 - 3. Treatment discontinuation due to lack of EVR (HCV RNA < 1 log drop at week 12 ontreatment) or
 - 4. Premature discontinuation due to intolerable adverse effects.

A complete medication (including prescribed medications, OTC, supplements and herbal medications or drinks) history must be assessed, including start and stop dates. Any allergies to any medications and their formulations must be documented. Potential drug-drug interactions should be checked with the current updated www.hep druginteractions.org (see section 9.3).

